### **3.4. Number of Planned Patients**

Approximately 30 patients are planned for randomization in this study.

### **3.5. Method of Assigning Patients to Treatment Groups**

Using the Interactive Response System (IRS), patients will be randomized 2:1 to the cemdisiran or placebo arms. Randomization will be stratified by baseline urine proteinuria levels ( $\geq 1$  g/24h and  $< 2$  g/24h versus  $\geq 2$  g/24h).

Each patient will be uniquely identified in the study by a combination of the site number and patient identification number. Upon signing the informed consent form (ICF), the patient will be assigned a patient identification number by the IRS. The Investigator or his/her designee will contact the IRS after confirming that the patient fulfills all the inclusion criteria and none of the exclusion criteria at Screening and prior to randomization.

### **3.6. Blinding**

All site personnel including sponsor delegated clinical research associates, data management CRO and patients will be blinded to study drug treatment during the efficacy period (up to Week 36). Sponsor personnel will not be blinded to study treatment. Cemdisiran and placebo will be packaged identically. The study drug will be administered under the supervision of the Investigator or at the patient's home by a healthcare professional (see Section 5.2.2). Since cemdisiran may be visually distinguishable from placebo, the syringe will be masked by a site pharmacist prior to administration by a healthcare professional. See the Pharmacy Manual for additional details. Further details on blinding and unblinding arrangements will be documented in a separate plan /manual.

#### **3.6.1. Emergency Unblinding**

If the treating physician determines that the clinical management of the patient requires knowledge of the study drug assignment, the Investigator may break the blind, as necessary. If time permits, clinical study center personnel should contact the Medical Monitor before unblinding to discuss the need to unblind the patient but must do so within 1 working day after the unblinding event. A record of when the blind was broken, who was unblinded, who broke the blind, and why it was broken, will be maintained in the Trial Master File (TMF).

Further details on blinding and unblinding arrangements will be documented in a separate plan / manual.

### **3.7. Data Monitoring Committee**

An independent DMC will perform regular reviews of safety, tolerability, and immunogenicity data throughout the study with the primary purpose of protecting the safety of participating patients and the integrity of the study. The DMC will operate under the rules of a Charter that will be reviewed and approved at the organizational meeting of the DMC. The DMC will perform periodic reviews of unblinded data (safety, tolerability, PK, pharmacodynamics (PD), ADA, circulating immune complexes (CIC) and efficacy of cemdisiran) during the clinical trial, and on an ad hoc basis review emergent safety data. Details are provided in the DMC Charter.

## 4. SELECTION AND WITHDRAWAL OF PATIENTS

### 4.1. Inclusion Criteria

Patients are eligible to be included in the study if all the following criteria apply:

#### Age and Sex

1. Male or female  $\geq 18$  years and  $\leq 65$  years of age at the time of informed consent

#### Patient and Disease Characteristics

2. Clinical diagnosis of primary IgAN as demonstrated by historical biopsy collected within 60 months of Screening
3. Treated for IgAN with stable, optimal pharmacological therapy. In general, stable and optimal treatment will include maximum allowed or tolerated ACE inhibitor or an ARB for at least 3 months prior to start of run-in period
4. Urine protein  $\geq 1$  g/24-hour at Screening and mean urine protein  $\geq 1$  g/24-hour from two valid 24-hour urine collections at the end of the run-in period, prior to randomization
5. Hematuria as defined by  $\geq 10$  RBCs per high powered field (RBC/hpf) at Screening
6. Females of child-bearing potential must have a negative pregnancy test, cannot be breast feeding, and must be willing to use a highly effective method of contraception 14 days before first dose, throughout study participation, and for 90 days after last dose administration
7. Previously vaccinated with meningococcal group ACWY conjugate vaccine and meningococcal group B vaccine or willingness to receive these vaccinations as well as prophylactic antibiotic treatment, if required by local standard of care
8. Previously vaccinated or willingness to receive vaccinations for Hib and *Streptococcus pneumoniae* according to current national/local vaccination guidelines for vaccination use

#### Informed Consent

9. Patient is willing and able to provide written informed consent and to comply with the study requirements

### 4.2. Exclusion Criteria

Patients are excluded from the study if any of the following criteria apply:

#### Disease-specific Conditions

1. Concomitant significant renal disease other than IgAN
2. A diagnosis of rapidly progressive glomerulonephritis as measured by eGFR loss  $>30\%$  over the duration of the run-in phase
3. Secondary etiologies of IgAN (eg, inflammatory bowel disease, celiac disease)
4. Diagnosis of Henoch-Schonlein Purpura (IgA Vasculitis)

5. eGFR <30 mL/min/1.73 m^2 2 weeks prior to randomization (local results will be used for assessment of eligibility)

### **Laboratory Assessments**

6. Has any of the following laboratory parameter assessments:
  - a. Alanine transaminase (ALT) >1.5×upper limit of normal (ULN), International Normalized Ratio (INR) >2 (or >3.5 if on anticoagulants), or total bilirubin >1.5×ULN (unless bilirubin elevation is due to Gilbert's syndrome)
7. Confirmed positive IgG/IgM/IgA ADAs to cemdisiran at Screening
8. Clinical laboratory test results considered clinically relevant and unacceptable in the opinion of the Investigator
9. Known human immunodeficiency virus (HIV) infection, hepatitis C virus (HCV) infection or hepatitis B virus (HBV) infection

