### **Medical Conditions**

12. Malignancy (except for non-melanoma skin cancers, cervical in situ carcinoma, breast ductal carcinoma in situ, or stage 1 prostate cancer) within the last 5 years
13. Active psychiatric disorder, including, but not limited to schizophrenia, bipolar disorder, or severe depression despite current pharmacological intervention
14. Known medical history or evidence of chronic liver disease or cirrhosis
15. Has other medical conditions or comorbidities which, in the opinion of the Investigator, would interfere with study compliance or data interpretation
16. History of multiple drug allergies or history of allergic reaction to an oligonucleotide or GalNAc
17. History of intolerance to SC injection(s) or significant abdominal scarring that could potentially hinder study drug administration or evaluation of local tolerability
18. Known contraindication to meningococcal vaccines (group ACWY conjugate and group B vaccines) required for this study. Refer to the most recent local product information for each vaccine for the current list of contraindications
19. Unable to take antibiotics for meningococcal prophylaxis, if required by local standard of care
20. Sustained blood pressure >140/90 mmHg as defined by 2 or more readings during the run-in period, measured in supine position after 10 minutes of rest

21. Receipt of an organ transplant (including hematologic transplant)
22. History of meningococcal infection within 12 months before Screening
23. Patients with systemic bacterial or fungal infections that require systemic treatment with antibiotics or antifungals
24. Patients with functional or anatomic asplenia

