### 5.2.3.1. LFT Criteria for Withholding, Monitoring and Stopping Cemdisiran Dosing

1. LFT results ([Table 5](#)) from the previous visit should be reviewed prior to dosing. Central laboratory results are preferable. If not available, local laboratory results may be used; however, if a local assessment is drawn, a serum chemistry sample must also be drawn for analysis at the central laboratory.
2. For any ALT or AST elevation  $>3 \times \text{ULN}$ , central laboratory results should be used to guide subsequent monitoring as detailed in [Table 4](#).
3. For any ALT or AST elevation  $>3 \times \text{ULN}$ :
  - a. Confirm using central laboratory, as soon as possible, ideally within 2 to 3 days, but no later than 7 days.
  - b. Perform assessments per [Table 4](#) and [Table 6](#).
  - c. If an alternative cause is found, provide appropriate care.
4. For any ALT or AST elevation  $>3 \times \text{ULN}$  without alternative cause that is accompanied by clinical symptoms consistent with liver injury (eg, nausea, right upper quadrant abdominal pain, jaundice) or elevated bilirubin to  $\geq 2 \times \text{ULN}$  or INR  $\geq 1.5$ , permanently discontinue dosing.
5. For confirmed ALT or AST elevations  $>3 \times \text{ULN}$  without alternative cause and not accompanied by symptoms or elevated bilirubin  $\geq 2 \times \text{ULN}$  or INR  $\geq 1.5$ , see [Table 4](#)

**Table 4: Monitoring and Dosing Rules for Asymptomatic Patients with Confirmed Isolated Elevations of ALT and/or AST  $>3\times$  ULN, with No Alternative Cause Identified**

Transaminase Level	Action
$>3\times$ to $5\times$ ULN	

May continue dosing

Evaluate the initial elevation in LFT per the following assessments:

Table 6 (all assessments to be performed once)

Hematology, serum chemistry, LFT, and coagulation per Table 5

Monitor at least every two weeks: LFT and coagulation per Table 5

If elevation persists for <math>\geq 2</math> months, must discuss with the Medical Monitor before continuing dosing

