$>5\times$ to $8\times$ ULN	

Hold cemdisiran dosing until recovery to <math>\leq 1.5\times</math>ULN; may resume dosing after discussion with the Medical Monitor

Evaluate the initial elevation in LFT per the following assessments

Table 6 (all assessments to be performed once)

Hematology, serum chemistry, LFT, and coagulation per Table 5

Monitor at least weekly: LFT and coagulation per Table 5 until ALT and/or AST is declining on 2 consecutive draws, then may decrease monitoring to biweekly

If ALT or AST rises to <math>>5\times</math>ULN following resumption of dosing, permanently discontinue dosing

$>8\times$ ULN	Permanently discontinue dosing after confirmation of the transaminase value

Abbreviations: ALT=alanine transaminase; AST=aspartate transaminase; INR=international normalized ratio; LFT=liver function test(s); ULN=upper limit of normal.

Notes: In addition to these criteria, other assessments or evaluations may be performed per Investigator discretion, as appropriate.

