### Adverse Events of Clinical Interest

Based on the biological target and the available nonclinical and clinical data, AEs of Clinical Interest (AECI) for this study are:

- Severe infections as judged by the investigator
- ALT or AST  $>3\times$ ULN
- Severe or serious injection site reactions (ISRs); ISRs that are associated with a recall phenomenon (reaction at the site of a prior injection with subsequent injections), or those that lead to temporary dose interruption or permanent discontinuation of cemdisiran.

An ISR is defined as a local reaction at or near the site of injection. “At or near” the injection site includes reactions at the injection site, adjacent to the injection site, or a reaction which may shift slightly away from the injection site due to gravity (eg, as may occur with swelling or hematoma). A systemic reaction which includes the injection site (eg, generalized urticaria, other distinct entities or conditions like lymphadenopathy that may be near the injection site) is not considered an ISR.

For information on recording and reporting of AECIs, see Section 6.7.6.2 and Section 6.7.6.3 , respectively.

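### Exclusion criterion 6a sets no entry limit for AST, although the on-study liver rules act on ALT or AST

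*Protocol*

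**What the plan says.** In the current protocol (Amendment 2), exclusion criterion 6 in Section 4.2 has one item, 6a. It excludes patients with "Alanine transaminase (ALT) >1.5×upper limit of normal (ULN), International Normalized Ratio (INR) >2" (3.5 for those on anticoagulants) or with total bilirubin above 1.5×ULN unless due to Gilbert's syndrome. AST is not named. The Amendment 1 and initial protocol versions word this item the same way.

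Three other exclusions could reach an isolated AST elevation, none with a number:

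- criterion 8, laboratory results that the investigator finds clinically relevant and unacceptable;
- criterion 14, "Known medical history or evidence of chronic liver disease or cirrhosis";
- criterion 15, "Has other medical conditions or comorbidities which, in the opinion of the Investigator, would interfere with study compliance or data interpretation".

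On study, ALT and AST are treated as a pair. Section 5.2.3.1 item 3 says of either one above 3×ULN: "Confirm using central laboratory, as soon as possible, ideally within 2 to 3 days, but no later than 7 days", with the assessments in Tables 4 and 6 to follow. Table 4 is headed "Monitoring and Dosing Rules for Asymptomatic Patients with Confirmed Isolated Elevations of ALT and/or AST" above 3×ULN with no alternative cause. Its row for >3× to 5×ULN reads "May continue dosing". Its row for >5× to 8×ULN reads "Hold cemdisiran dosing until recovery to" 1.5×ULN or below. Above 8×ULN, dosing stops permanently once the value is confirmed. Section 6.7.6.1 states which "AEs of Clinical Interest (AECI) for this study are", and ALT or AST above 3×ULN is on that list.

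**The concern.** Entry is the one step in the liver-safety scheme where AST drops out. A patient can pass every numeric limit and yet, before any study drug, already be at the level that triggers confirmation, work-up and the event-of-interest definition.

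Section 1.5 (in the Amendment 1 text; the part of Amendment 2 that holds the matching paragraph is not shown) names liver function test abnormality as one of three important potential risks and notes that the drug is directed to the liver. Two things are at stake. First, a patient already in the work-up range could receive a first dose unless an investigator steps in. Second, an AST above 3×ULN seen on study would not necessarily reflect a change on study. Section 3.1 plans about 20 cemdisiran and 10 placebo patients, so one such patient is 1/20 = 5% of the active arm or 1/10 = 10% of the placebo arm.

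The point does not assume that criterion 6a was meant to mirror Table 4, nor that an unchanged pre-dose value would be counted as an adverse event.

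**Working it through.** The protocol states no figure to reproduce. The check compares its own thresholds, all in multiples of ULN.

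| Test | Entry limit (criterion 6a) | First on-study action level (Section 5.2.3.1 and Section 6.7.6.1) | Rise needed from the entry limit |
|---|---|---|---|
| ALT | 1.5 | above 3.0 | 3.0 / 1.5 = 2.0-fold |
| AST | none | above 3.0 | none, if entry AST is already above 3.0 |

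**Can a patient enter above the action level?** Take ALT at or below 1.5×ULN, INR at or below 2, total bilirubin at or below 1.5×ULN and AST above 3×ULN. No numeric limit in criterion 6a is breached. Criteria 8, 14 and 15 apply only if the investigator judges that they do.

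**Does the pre-dose review close the gap?** Section 5.2.3.1 item 1 has the previous visit's liver tests reviewed before dosing, and AST belongs to the Table 5 liver panel. The outcome depends on the level:

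- AST >3× to 5×ULN, confirmed, isolated, without symptoms or alternative cause: Table 4 allows dosing, with liver and coagulation tests at least every two weeks.
- AST >5× to 8×ULN, under the same conditions: dosing is held until recovery to 1.5×ULN or below.
- AST above 8×ULN, under the same conditions: permanent stop after confirmation.
- AST above 3×ULN without alternative cause but with symptoms of liver injury, bilirubin at or above 2×ULN, or INR at or above 1.5: permanent stop (item 4).

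The review therefore catches the higher or complicated cases. It does not prevent a first dose in the >3× to 5×ULN band.

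**Is AST available at entry?** Yes. It is listed in Table 5, and Section 6.1 includes the clinical laboratory assessments at Screening.

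**The case against.** The strongest reply is that nothing is misstated. Entry limits and on-study dosing rules serve different ends and need not cover the same tests, and a limit on ALT, bilirubin and INR backed by a laboratory discretion clause is a defensible choice. Several safeguards also apply:

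- Laboratory tests are done at Screening, during the run-in and before dosing on Day 1, when eligibility is reassessed (Sections 6.1 to 6.3).
- An AST persistently above 3×ULN would raise criterion 14. Criteria 9 (viral hepatitis and HIV) and 25 (alcohol) narrow the group further.
- Table 4 itself accepts dosing with monitoring in the >3× to 5×ULN band.
- Section 7.2.8 reports laboratory changes from baseline and shifts to the worst value, and there is a placebo arm. A high starting value would be visible.

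Much of this stands. The case will be rare, and the baseline-referenced tables would help to interpret it. None of it supplies an AST limit, however. Discretion covers ALT, INR and bilirubin too, and the sponsor still gave those three a number. Discretion can also differ between sites, and the Amendment 1 synopsis plans 30 to 40 centers for about 30 patients. Table 4 governs patients already on study drug; letting them continue under monitoring is a different decision from starting a patient who is already in that range. Shift tables describe a raised baseline after the fact and do not keep the patient from being dosed.

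**Conclusion.** The concern holds, as a minor point. Criterion 6a limits three liver-related tests and leaves out AST, so a patient can satisfy every numeric limit with AST already above the 3×ULN action level. Within the >3× to 5×ULN band, the dosing rules then permit treatment.

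This conclusion rests only on the protocol's own thresholds. How often it would matter cannot be computed, because the documents give no frequency for isolated AST elevation in this population; it is assumed to be low. Sample size, the primary endpoint and the efficacy analysis are not affected.

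**What to change.** In Section 4.2, extend the first limit of criterion 6a to read: ALT or AST >1.5×ULN. The value is one the protocol already uses, for ALT at entry and for ALT or AST recovery in the >5× to 8×ULN row of Table 4.

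The cost is two words in one criterion. No test or visit is added. The downside is an occasional extra screen failure, which the single retest allowed by Section 6.1.2 for transient laboratory abnormalities would limit.

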### **Prior/Concomitant Therapy**

10. Treatment with systemic steroids for more than 7 days or other immunosuppressant agents in the 12 months prior to randomization
11. Received an investigational agent within the last 30 days or 5 half-lives, whichever is longer, prior to the first dose of study drug, or are in follow-up of another clinical study prior to study enrollment

### **Medical Conditions**

12. Malignancy (except for non-melanoma skin cancers, cervical in situ carcinoma, breast ductal carcinoma in situ, or stage 1 prostate cancer) within the last 5 years
13. Active psychiatric disorder, including, but not limited to schizophrenia, bipolar disorder, or severe depression despite current pharmacological intervention
14. Known medical history or evidence of chronic liver disease or cirrhosis
15. Has other medical conditions or comorbidities which, in the opinion of the Investigator, would interfere with study compliance or data interpretation
16. History of multiple drug allergies or history of allergic reaction to an oligonucleotide or GalNAc
17. History of intolerance to SC injection(s) or significant abdominal scarring that could potentially hinder study drug administration or evaluation of local tolerability
18. Known contraindication to meningococcal vaccines (group ACWY conjugate and group B vaccines) required for this study. Refer to the most recent local product information for each vaccine for the current list of contraindications
19. Unable to take antibiotics for meningococcal prophylaxis, if required by local standard of care
20. Sustained blood pressure >140/90 mmHg as defined by 2 or more readings during the run-in period, measured in supine position after 10 minutes of rest

21. Receipt of an organ transplant (including hematologic transplant)
22. History of meningococcal infection within 12 months before Screening
23. Patients with systemic bacterial or fungal infections that require systemic treatment with antibiotics or antifungals
24. Patients with functional or anatomic asplenia

### **Alcohol Use**

25. Patients who consume more than 14 units of alcohol a week (unit 1 glass of wine [125 mL] = 1 measure of spirits [approximately 1 fluid ounce] =  $\frac{1}{2}$  pint of beer [approximately 284 mL])

## **4.3. Removal from Therapy or Assessment**

Patients or their legal guardians are free to discontinue study drug and/or stop participation in the study at any time and for any reason, without penalty to their continuing medical care. The Investigator or the Sponsor may stop a patient's participation in the study at any time if this is considered to be in the patient's best interest. Any discontinuation of treatment or the stopping of the patient's participation in the study must be fully documented in the electronic case report form (eCRF) and should be followed up by the Investigator.

Discontinuation of study drug is described in Section 4.3.1, while the stopping of a patient's participation in the study is detailed in Section 4.3.2.

### **4.3.1. Discontinuation of Study Drug or Declining Procedural Assessments**

Reasons for discontinuation of study drug include any of the following:

- Significant violation of the protocol
- Adverse event
- Non-adherence to treatment regimen
- Pregnancy
- Lost to follow-up
- Other reason (non-adverse event), including confirmed positive test for ADA to cemdisiran
- Or, study is terminated by the Sponsor

Patients who are pregnant will be discontinued from study drug dosing immediately (see Section 6.7.5.2 for reporting and follow-up of pregnancy). A positive urine pregnancy test should be confirmed by a serum pregnancy test prior to discontinuing study drug.

Patients who discontinue study drug and/or decline procedural assessments should not be automatically removed from study. In general, patients who discontinue study drug dosing for any reason will be encouraged to remain on the study to complete the remaining assessments through the Week 36/EOS or Week 84/OLE EOS visit and safety follow-up so that their experience is captured in the final analyses.

If this occurs, the Investigator is to discuss with the patient the appropriate processes for discontinuation from study drug and must discuss with the patient the options for continuation of the Schedule of Assessments ([Table 2](#)), including different options for follow-up and collection of data (eg, in person, by phone, by mail, through family or friends, or from options not involving patient contact, such as communication with other treating physicians or from review of medical records), including endpoints and adverse events, and must document this decision in the patient's medical records.

If a patient discontinues dosing due to an AE, including SAEs, the event should be followed as described in Section [6.7.6](#). When a patient discontinues study drug dosing, the primary reason must be recorded in the eCRF. Patients who discontinue study drug and remain on study may receive treatment consistent with local standard practice for their disease per Investigator judgement, as applicable.

Patients who discontinue from study drug during the 36-week treatment period (defined as the time the first dose of study drug is administered on Study Day 1 through completion of the Week 36 assessments) will be encouraged to remain on the study and complete assessments through Week 36; they will also be asked to complete safety follow-up visits 13, 26, 39 and 52 weeks thereafter (see [Table 1](#)).

Patients who discontinue study drug during the OLE period will be asked to return for their next scheduled visit to complete the OLE EOS/ET assessments; they will also be asked to complete safety follow-up visits 13, 26, 39 and 52 weeks thereafter (see [Table 2](#)).

